2.2. Study Endpoints

Primary Endpoints:

IRNF:

- Sensitivity of the irregular rhythm notification for the identification of persons with AF by 13-day ambulatory ECG, with AF defined as at least 30 seconds of AF by ambulatory ECG.
- Specificity of the lack of irregular rhythm notification for the identification of persons without AF by 13-day ambulatory ECG, with AF defined as at least 30 seconds of AF by ambulatory ECG.

AFBF:

- Weekly AF burden estimate, defined as the percentage of time a subject is in Atrial Fibrillation during wrist device wear over the prior 7 consecutive days

Secondary Endpoints:

IRNF:

- Notification-level positive predictive value (PPV) with AF by ambulatory ECG at the time of any tachogram comprising the notification.
- Tachogram-level performance (Sensitivity, Specificity, false positive rate (FPR), PPV, negative predictive value (NPV)) for tachograms comprising alerts.
- Tachogram-level performance (Sensitivity, Specificity, FPR, PPV, NPV) for all generated tachograms.

AFBF:

- Sensitivity, specificity, positive predictive value, and negative predictive value of tachograms for the identification of AF by ambulatory ECG.
- Day-specific AF burden estimate defined as the percentage of time a subject is in Atrial Fibrillation during a specific day of the week.
- Four-hour segment-specific AF burden estimate defined as the percentage of time a subject is in Atrial Fibrillation during a specific four-hour segment of a day.

Study Hypotheses

IRNF:

The primary endpoint hypothesis associated with the IRNF is:

[REDACTED]

[REDACTED] Data from subjects in Cohorts 1, 3, and 4 will be used to test this hypothesis.

The secondary endpoint hypothesis associated with the IRNF compares the tachogram-level false positive rate (FPR) of the test device to that of the predicate device to determine if the test device algorithm FPR is non-inferior [REDACTED] to that of the predicate device using all tachograms generated only from subjects in Cohort 2 (Aggressor Rhythm Cohort). [REDACTED]

[REDACTED]

AFBF:

The primary endpoint hypothesis associated with the AFBF is:

[REDACTED]

The secondary endpoint hypotheses associated with the day-specific and four-hour segment-specific endpoints are listed below, respectively:

[REDACTED]

[REDACTED]
[REDACTED]
[REDACTED]
[REDACTED] Additional
information on the simulation methodology is contained in Section 6.2.3 and the SAP.

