6.2. Statistical Methodology

For all of the IRNF statistical analyses, atrial fibrillation (AF) and atrial flutter (AFL) will be treated as a single category of "AF". For all of the AFBF statistical analyses, atrial fibrillation (AF) will be considered its own unique category (i.e., atrial flutter will not be included as part of the detection of AF episodes).

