6.2.3. Secondary Endpoint Analyses

IRNF

The notification-level PPV of AF by ambulatory ECG at the time of any tachogram comprising the notification will be estimated for both the test and predicate device algorithms. The notification-level PPV is defined as the proportion of notifications where at least one of the ECG strip results associated with the spot tachograms that comprise the notification exhibits AF of at least 10 seconds per the ECG strip diagnosis definition presented in Section 5.5.2.1.

Notification-Level PPV = (# of notifications with an adjudicated ECG strip diagnosis of AF of at least 10 seconds for any tachogram comprising the notification) / (# of alert notifications)

For subjects who exhibit a high level ($\geq 95\%$) AF burden, it is expected that a large (100 to 200) number of notifications will be generated in total for both the IRN 1.0 and 2.0 algorithms resulting in $>1,000$ tachograms per subject in Cohort 4. For these subjects who are permanently in AF, a least burdensome approach will be followed where for all notifications generated from subjects in Cohorts 1 and 3 and randomly selected notifications from subjects in Cohort 4 will be included in this analysis. A corresponding adjudicated ECG strip diagnosis will be determined for all tachograms comprising these notifications.

Because the set of notifications may differ between the test and predicate device algorithms and because multiple notifications may be associated with some subjects, a bootstrap approach will be implemented to obtain 95% two-sided confidence intervals separately for each algorithm's notification-level PPV. The bootstrap sampling will randomly select subjects who have analyzable data with replacement rather than individual data points to account for any correlation structure that might exist within subjects so that confidence limits are corrected for within-subject correlation.

Two tachogram-level analysis results

associated with the secondary endpoints

of tachogram performance will be reported separately for each device algorithm using tachograms generated by subjects in Cohorts 1, 3, and 4. Separate contingency tables cross-classifying the adjudicated cardiologist diagnoses from ECG strips with the binary classification of tachogram results for test and predicate devices will be presented as outlined in [Table 7](#) below.

Table 7: Cross-Classification Table of Tachogram Results and Adjudicated Cardiologist Diagnoses from ECG Strips

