Tachogram Result	Adjudicated Cardiologist Diagnosis					Total
	SR	AF	Atrial Flutter	Other Irregular Rhythm	Uninterpretable	
Irregular	n11	n12	n13	n14	n15	nTI
Not AF	n21	n22	n23	n24	n25	nTN
Total	nSR	nAF	nAFL	nOA	nU	N

Abbreviations: SR = sinus rhythm; AF=atrial fibrillation; AFL=atrial flutter

Tachogram performance for the test and predicate devices will be estimated separately as outlined below because the set of tachograms will differ by device. Two-sided 95% bootstrap confidence intervals will be constructed for each performance metric by randomly selecting subjects who have analyzable data with replacement to account for any within subject correlation of multiple tachograms associated with each subject.

Tachogram Sensitivity = $(n12+n13)/(nAF+nAFL)$

Tachogram Specificity = $n21/nSR$

Tachogram False Positive Rate = $(n11+n14)/(nSR+nOA)$

Tachogram PPV = $(n12+n13)/(nTI-n15)$

Tachogram NPV = $n21/(nTN-n25)$

The ECG strips corresponding to all tachograms which comprise each notification for subjects in Cohorts 1, 3 and 4 from the test and predicate device algorithms will be adjudicated and included in the analysis of this secondary endpoint.

AFBF

A tachogram-level analysis associated with the secondary endpoint of tachogram performance for the AFBF will be reported by cross-classifying the binary classification of tachogram results with the adjudicated cardiologist classifications from ECG strips where the SR and Other Abnormal Rhythm adjudications are combined into a single category. [REDACTED]

Using the notation of [Table 7](#), tachogram performance will be estimated as outlined below from the randomly selected tachograms for all subjects in Cohorts 3 and 4. Two-sided 95% bootstrap confidence intervals will be constructed for each performance metric to account for potential within subject correlation of the multiple tachograms associated with each subject.

- Tachogram Sensitivity = $n12/nAF$
- Tachogram Specificity = $(n21+n23+n24)/(nSR+nAFL+nOA)$
- Tachogram PPV = $n12/(nTI-n15)$
- Tachogram NPV = $(n21+n23+n24)/(nTN-n25)$

Although the set of tachograms for the AFBF device algorithm will differ from the set of tachograms generated from the test IRNF device algorithm, [REDACTED]

[REDACTED] The same tachogram performance analysis of the AFBF device algorithm will be performed as specified above.

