6.2.5. Additional Analyses

Subject accountability, device accountability, medical history, medication, demographic and baseline characteristics will be summarized by final cohort assignment for the reporting of results for the subjects included in the evaluation of the IRNF and AFBF devices. The final cohort assignments for subjects who self-report at the time of screening in Cohorts 1, 3, and 4 will be determined based on their final adjudicated reference ECG results of AF burden as follows:

- Cohort 1: Adjudicated AF Burden via reference ECG of 0%
- Cohort 3: Adjudicated AF Burden via reference ECG of >0% to <95%
- Cohort 4: Adjudicated AF Burden via reference ECG of $\geq 95\%$

The final cohort assignment of subjects who self-report at the time of screening in Cohort 2 will remain Cohort 2. If an adjudicated AF Burden measurement cannot be determined for a subject, the final cohort designation will be the same as the self-reported cohort at the time of screening. The rationale for reporting the results by final cohort designation is to most closely align the reporting of results based on the presentation or absence of AF during the study monitoring period regardless of prior diagnosis.

Additional efficacy analyses are described below.

IRNF

The performance at the person- and notification-level for AF and other arrhythmias (treated as a single combined category) by ambulatory ECG will be analyzed similarly to the corresponding primary and secondary endpoint analyses outlined above for the adjudicated diagnoses of only AF using all available data for subjects in Cohorts 1, 3, and 4. These additional analyses are distinct from the primary and secondary endpoint analyses in that the AF and other arrhythmia categories of diagnoses presented in Section 5.5.2.1 will be combined into a single category for purposes of analysis. In particular, the following performance parameters will be estimated and presented along with their associated 95% confidence intervals.

1. Sensitivity of the IRNF for the identification of persons for AF or other arrhythmias by up to 13-day (± 2 days) ambulatory ECG, defined as at least 10 seconds of AF or other arrhythmia by ambulatory ECG
2. Specificity of the lack of IRNF for the identification of persons without AF or other arrhythmias by up to (± 2 days) 13-day ambulatory ECG, defined as at least 10 seconds of AF or other arrhythmia by ambulatory ECG

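### The IRNF tachogram NPV formula scores correct negatives on other-irregular-rhythm strips as failures, so the reported NPV is too low by n24/(nTN − n25)

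*Combined protocol and SAP*

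**What the plan says.** Section 2.2 lists as an IRNF secondary endpoint "Tachogram-level performance (Sensitivity, Specificity, FPR, PPV, NPV) for all generated tachograms", and lists the same five metrics for the tachograms that make up alerts. Under Section 6.2.3 the results "will be reported separately for each device algorithm using tachograms generated by subjects in Cohorts 1, 3, and 4".

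Table 7 crosses the device result (Irregular, Not AF) with five adjudicated categories: sinus rhythm, AF, atrial flutter, other irregular rhythm and uninterpretable. The IRNF NPV is then "Tachogram NPV = $n21/(nTN-n25"). The false positive rate in the same list is ("n11+n14)/(nSR+nOA"), and specificity is n21/nSR. The AFBF NPV, in the same notation, is ("n21+n23+n24)/(nTN-n25").

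Section 6.2 fixes the target condition: "For all of the IRNF statistical analyses, atrial fibrillation (AF) and atrial flutter (AFL) will be treated as a single category of" AF. Section 5.5.2.1.1 assigns a strip to the other-arrhythmia class when it shows an arrhythmia that is not AF. On precision, two-sided 95% "bootstrap confidence intervals will be constructed for each performance metric by randomly selecting subjects who have analyzable data with replacement".

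**The concern.** An NPV for AF should answer one question: among readable tachograms called Not AF, what fraction truly had no AF or flutter? The written formula gives the fraction that were in sinus rhythm. It falls when AF is missed, as it should. It also falls with every other-rhythm strip that the device rightly rejects.

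Two things follow. A device that makes no errors scores below 100%. And a device that is better at rejecting other rhythms has more n24 in its denominator and so a lower NPV, which means the side-by-side test and predicate figures can point the wrong way.

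The n24 cell need not be small. The classification steps in Section 5.5.2.1.1 send sinus rhythm with PACs, PVCs or junctional beats, and sinus arrhythmia, to the other class, and that step sets no frequency threshold. On the other hand, the aggressor-rhythm Cohort 2 does not contribute to this analysis.

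**Working it through.** **1. Expand the denominator (Table 7, Not AF row).** nTN = n21 + n22 + n23 + n24 + n25, so nTN − n25 = n21 + n22 + n23 + n24.

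**2. Classify the cells under the Section 6.2 target (AF plus flutter).** Missed positives are n22 and n23. Correct negatives are n21 and n24.

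**3. Compare the two formulas.**
- Written: n21/(n21 + n22 + n23 + n24)
- NPV for AF plus flutter: (n21 + n24)/(n21 + n22 + n23 + n24) = 1 − (n22 + n23)/(nTN − n25)
- Difference: n24/(nTN − n25)

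**4. Check against the rest of the list.** The IRNF false positive rate has n14 in its numerator and nOA in its denominator, so other rhythms are negatives; its complement is (n21 + n24)/(nSR + nOA). The IRNF PPV, (n12 + n13)/(nTI − n15), counts n14 as a non-success. The AFBF NPV credits n24.

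**5. Error-free device.** With n22 = n23 = 0, n21 = nSR and n24 = nOA, the written NPV is nSR/(nSR + nOA), however many AF strips there are. The correct value is 100%.

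**6. Size on assumed counts.** The documents give no tachogram counts. Assume 10,000 non-AF strips, 1,000 to 10,000 AF strips, 95% sensitivity, and false positives of 0.2% in sinus rhythm and 2% to 10% in other rhythms.

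| Other share of non-AF strips | Written NPV, error-free device | Shortfall (points) | Written NPV, 3,000 AF strips | Corrected NPV, 3,000 AF strips |
|---|---|---|---|---|
| 5% | 95% | 4.3–4.9 | 93.7–94.1% | 98.5% |
| 10% | 90% | 8.7–9.8 | 88.8–89.5% | 98.5% |
| 20% | 80% | 17.5–19.6 | 79.1–80.4% | 98.5% |
| 30% | 70% | 26.5–29.5 | 69.3–71.0% | 98.5% |

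If n24 were only 1% of readable Not AF tachograms, the shortfall would be 1 point.

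**7. Ordering.** Assume 8,000 sinus, 2,000 other and 3,000 AF strips, with 0.2% false positives in sinus rhythm, so n21 = 8,000 × 0.998 = 7,984 for both devices.
- Device A, 93% sensitivity and 10% false positives in other rhythms: n22 + n23 = 210, n24 = 1,800, denominator 9,994. Written 7,984/9,994 = 79.9%; corrected 9,784/9,994 = 97.9%.
- Device B, 95% and 2%: n22 + n23 = 150, n24 = 1,960, denominator 10,094. Written 7,984/10,094 = 79.1%; corrected 9,944/10,094 = 98.5%.

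B is better on both error rates and scores lower as written.

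**8. Specificity label.** n21/nSR minus (1 − FPR) equals the other share times the difference between the false-positive rates in other rhythms and in sinus rhythm. On the assumptions of step 6 this runs from 5% × 1.8 points = 0.1 to 30% × 9.8 points = 2.9 points. It is zero if the two rates are equal.

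**The case against.** The strongest defence is that the formula follows another convention. If the condition were AF or any other arrhythmia, with sinus rhythm as the only negative, then n21/nSR and n21/(nTN − n25) would both be right. Listing specificity and false positive rate separately would also make more sense if they used different negative classes.

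This does not hold for the list as a whole. Under that condition sensitivity and PPV would have to credit n14, and the false positive rate would be n11/nSR; none is written so. On pooling AF with other arrhythmias, Section 6.2.5 also says: "These additional analyses are distinct from the primary and secondary endpoint analyses in that the AF and other arrhythmia categories of diagnoses presented". The rest of that sentence merges the two categories into one. The parameters it then lists are at person and notification level, so it does not address tachogram NPV by name, but it does say that pooling is what separates those analyses from the secondary endpoints. A sinus-rhythm-only convention does not rescue the formula either, because n24 would then leave the denominator too. With n24 at 20% and missed AF at 1% of readable Not AF tachograms, that version gives 0.9875, the AF-plus-flutter version 0.99, and the written one 0.79.

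Several points do stand:
- The direction is conservative for both devices, and the readable text plans no test on NPV.
- NPV depends on case mix and the two tachogram sets differ, so even a corrected NPV would not rank the devices cleanly. The ordering example shows what can happen, on invented error rates.
- A reader can rebuild the point estimate from Table 7. Section 6.2.5 also reports the probability of an other rhythm given Not AF, with an interval, for the randomly selected tachograms. If that sample underlies the all-tachogram endpoint, which redaction leaves open, the missing component is visible there. Neither output changes what is labelled NPV, and the subject-level bootstrap interval for the combined quantity cannot be recovered from pooled counts.
- Text near these formulas is redacted, so a label for the specificity convention may exist out of sight.

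**Conclusion.** The concern holds. The formula is wrong as written for the stated target, and the shortfall of n24/(nTN − n25) is exact once other rhythms are treated as negatives, as the false positive rate in the same list treats them. Its numerical size is unknown: roughly 1 to 30 points over the assumed shares, depending almost entirely on how many other-rhythm strips occur. It should be corrected, but it affects only a descriptive secondary estimate and its interval for each device. The primary endpoints, the significance level and the Cohort 2 false-positive-rate comparison are untouched in the readable text. The specificity remark concerns labelling only; n21/nSR is a valid sinus-rhythm-only figure.

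**What to change.** Define IRNF tachogram NPV as (n21 + n24)/(nTN − n25) for both the alert and the all-tachogram analyses, and build the subject-level bootstrap interval on that definition. For specificity, either label n21/nSR as sinus rhythm only or report (n21 + n24)/(nSR + nOA), which is the complement of the stated false positive rate.

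The cost is one formula, one label and the matching bootstrap code, with no new data or adjudication. The corrected NPV is at least as high as the written one for each device, and higher whenever n24 is above zero. The change should therefore be made before results are seen, so that it cannot look driven by them.

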6.2.4. Safety Analyses

All adverse events (AEs) will be recorded throughout the entire study period, whether they are considered to be related to the study procedures or not. Signs and symptoms of each AE will be described in detail: date of event, description of event, severity, relationship to study procedures, action taken and outcome. AEs will be collected as spontaneously reported by the subjects.

AEs will be coded using MedDRA (latest version). The number of any AEs and the number and percentage of subjects reporting each type of adverse event will be presented by Preferred Term. Multiple occurrences of the same event reported by the same subject will be counted only once.

AE summaries (number of events and incidence) will be presented for all AEs, including the following:

- Serious adverse events (SAEs)
- Study procedure related AEs
- Severe AEs, which are AEs that are rated as Severe in intensity

Study procedure related AEs will include those events classified as possibly or definitely related to the study procedure.

6.2.5. Additional Analyses

Subject accountability, device accountability, medical history, medication, demographic and baseline characteristics will be summarized by final cohort assignment for the reporting of results for the subjects included in the evaluation of the IRNF and AFBF devices. The final cohort assignments for subjects who self-report at the time of screening in Cohorts 1, 3, and 4 will be determined based on their final adjudicated reference ECG results of AF burden as follows:

- Cohort 1: Adjudicated AF Burden via reference ECG of 0%
- Cohort 3: Adjudicated AF Burden via reference ECG of >0% to <95%
- Cohort 4: Adjudicated AF Burden via reference ECG of $\geq 95\%$

The final cohort assignment of subjects who self-report at the time of screening in Cohort 2 will remain Cohort 2. If an adjudicated AF Burden measurement cannot be determined for a subject, the final cohort designation will be the same as the self-reported cohort at the time of screening. The rationale for reporting the results by final cohort designation is to most closely align the reporting of results based on the presentation or absence of AF during the study monitoring period regardless of prior diagnosis.

Additional efficacy analyses are described below.

IRNF

The performance at the person- and notification-level for AF and other arrhythmias (treated as a single combined category) by ambulatory ECG will be analyzed similarly to the corresponding primary and secondary endpoint analyses outlined above for the adjudicated diagnoses of only AF using all available data for subjects in Cohorts 1, 3, and 4. These additional analyses are distinct from the primary and secondary endpoint analyses in that the AF and other arrhythmia categories of diagnoses presented in Section 5.5.2.1 will be combined into a single category for purposes of analysis. In particular, the following performance parameters will be estimated and presented along with their associated 95% confidence intervals.

1. Sensitivity of the IRNF for the identification of persons for AF or other arrhythmias by up to 13-day (± 2 days) ambulatory ECG, defined as at least 10 seconds of AF or other arrhythmia by ambulatory ECG
2. Specificity of the lack of IRNF for the identification of persons without AF or other arrhythmias by up to (± 2 days) 13-day ambulatory ECG, defined as at least 10 seconds of AF or other arrhythmia by ambulatory ECG
3. Notification-level PPV with AF and other arrhythmias by ambulatory ECG at the time of any tachogram comprising the notification

The false positive rate at the person-level for all subjects in Cohort 2 (Aggressor Rhythm Cohort) will also be reported. Using the notation of Table 6, the FPR for the test and predicate devices will be estimated as $(r+s)/N_2$ and $(r+t)/N_2$, respectively. Two-sided exact binomial confidence intervals associated with the FPRs will also be reported.

The following conditional probabilities computed using the randomly selected tachograms generated from subjects in Cohorts 1, 3, and 4 will be reported separately for the test and predicate devices along with their associated 95% two-sided bootstrap confidence intervals:

- $\Pr(\text{Device} = \text{Irregular} \mid \text{Reference} = \text{Other Irregular Rhythm})$;
- $\Pr(\text{Device} = \text{Not AF} \mid \text{Reference} = \text{Other Irregular Rhythm})$;
- $\Pr(\text{Device} = \text{Irregular} \mid \text{Reference} = \text{Uninterpretable})$;
- $\Pr(\text{Device} = \text{Not AF} \mid \text{Reference} = \text{Uninterpretable})$;
- $\Pr(\text{Reference} = \text{Other Irregular Rhythm} \mid \text{Device} = \text{Irregular})$;
- $\Pr(\text{Reference} = \text{Other Irregular Rhythm} \mid \text{Device} = \text{Not AF})$;
- $\Pr(\text{Reference} = \text{Uninterpretable} \mid \text{Device} = \text{Irregular})$;
- $\Pr(\text{Reference} = \text{Uninterpretable} \mid \text{Device} = \text{Not AF})$.

Contingency tables comparing the binary classification of randomly selected tachograms from the test and predicate devices will also be presented for each of the adjudicated cardiologist sub-category classifications of Other Abnormal Rhythm diagnoses presented in Section 5.5.2.1.

Contingency tables comparing the test and predicate device classifications (notification vs. no notifications at the subject-level) with each of the adjudicated cardiologist classifications of diagnoses presented in Section 5.5.2.1 including all sub-categories of the Other arrhythmia category will also be presented.

AFBF

A histogram will be produced for the paired differences in the weekly AFB average measurements. Boxplots of the weekly AFBF device measurements for ECG Patch categories of 0%, >0% to 33%, >33% to < 95%, $\geq 95\%$ will also be displayed.

The paired differences in the weekly AFB average measurements between the AFBF device and ambulatory ECG patch and corresponding two-sided 95% confidence intervals for the average paired difference will be presented for each of the following ranges of ambulatory ECG patch AFB categories:

- 0%
- >0% to 33%
- >33% to < 95%
- $\geq 95\%$

The false negative rate will be estimated as the number of subjects with a weekly AFBF device measurements = 0% and a paired ECG patch AFB measurement > 0% divided by the number of subjects with a paired ECG patch AFB measurement > 0%. A two-sided 95% exact binomial confidence interval for the false negative rate will also be reported.

A modified Bland-Altman analysis will be performed using only reference AF burden measurements which are strictly between 0% and 100%. In the analysis, the x-axis will be the reference burden and the y-axis will be the paired differences between the test device and reference method. Estimated limits of agreement and mean bias with associated 95% confidence interval) will be reported. No hypotheses will be tested in this analysis.

Medications (verbatim terms) will also be tabulated and reported.

